5.11.4. Subgroup Analyses

OS and PFS HR for treatment effect (with 95% CIs) will be estimated using an unstratified Cox PH model for each of the following subgroups (defined based on eCRF data):

- number of prior systemic therapies for advanced/metastatic disease (0 versus ≥ 1)
- prior systemic treatment in the neo-adjuvant or adjuvant setting (yes vs. no)
- histological tumor type (LMS vs. liposarcoma vs. undifferentiated pleomorphic sarcoma vs. other STS types)
- LMS primary site (uterine vs. non-uterine)
- ECOG performance status (0 vs. 1)
- region (North America vs. Europe vs. ROW)
- disease stage at randomization (metastatic disease versus only locally advanced disease)
- liver lesions (presence at baseline vs. absence at baseline)
- lung lesions (presence at baseline vs. absence at baseline)
- sex (females vs. males)
- age (< 65 years vs. ≥ 65 years)
- weight (above and below median)
- duration of disease since diagnosis (above and below median)
- grade of STS at diagnosis (1/low vs. 2/intermediate vs. 3/high)
- albumin level (above and below 35 g/dL)
- ALT (above and below median)
- bone lesions (presence at baseline vs. absence at baseline)
- prior radiation therapy (none vs. any)
- duration of most recent prior systemic therapy (above and below median)
- hemoglobin (above and below median)
- platelets (above and below 350 μ liters)
- leukocytes (above and below 10,000 μ liters)
- PDGFR α status (positive and negative [additional details in Section 5.16])

If a level of a factor consists of fewer than 5% of randomized patients, analysis within that level will be omitted. Additional subgroup analyses may be performed as deemed appropriate. The goal of subgroup analyses is to assess internal consistency of study results, and whether there is significant treatment heterogeneity across any of the subgroups. Appropriate interpretation is important since, even if all patient subgroups benefit to exactly the same extent in truth, smaller or larger estimated effects, even negative effects, may be seen for some subgroups simply by chance alone. Without appropriate interpretation, this can lead to erroneous conclusion in one or more subgroups, in particular where differential treatment effects are not expected across any of the factors assessed. In order to assist with interpretation of the subgroup results, the methodology of Fleming (1995) will be followed to provide background information on the extent of variability that might be expected by chance alone.

Additional exploratory subgroup analyses will consider specifically those histologic subtypes (listed immediately below) that are rare and/or possibly less responsive to chemotherapy with doxorubicin. Patient listings with efficacy outcomes will be generated for each of these subtypes. Summary analyses such as Kaplan-Meier or Cox modeling may be performed, either for the overall combination or certain combinations of these subtypes, depending on the number of patients with each of these subtypes.

- alveolar soft-part sarcoma
- synovial sarcoma
- clear cell sarcoma of soft tissue
- malignant solitary fibrous tumour
- PEComa NOS, malignant
- plexiform fibrohistiocytic tumour
- giant cell tumour of soft tissue
- extraskeletal myxoid chondrosarcoma
- angiosarcoma
- dedifferentiated liposarcoma

Selected analyses as listed below will be performed for subgroups gender (male vs. female), age group (<65 years vs. ≥65 years), and race (White vs. Black vs. Asian vs. All Other). ().

- overview of treatment-emergent AESIs
- summary of patient demographics and baseline characteristics
- summary of TEAEs by system organ class (SOC) and PT
- summary of TEAEs by worst CTCAE grade and PT
- summary of TEAEs by PT and decreasing frequency
- summary of TEAEs by consolidated category and PT

Additional subgroup analyses will be performed on the following variables if minimum of 40 subjects was achieved:

- age: <65 years, ≥65 years and <75 years, ≥75 years and <85 years, and ≥ 85 years

Patients demographic and baseline characteristics, drug exposure, key efficacy (OS, PFS, ORR), safety, and PRO variables will also be summarized for patients with no prior systemic therapies for advanced/metastatic disease.

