- [9] Availability of tumor tissue is mandatory for study eligibility. The patient must have consented to provide archived formalin-fixed paraffin embedded (FFPE) tumor tissue or be subject to a pre-treatment re-biopsy of primary or metastatic tumor tissue for future central pathology review and translational research (if archived tissue is unavailable) (refer to Section [10.4.2.3](#) regarding tissue collection parameters).
- [10] The patient has adequate hematologic, organ, and coagulation function within 2 weeks (14 days) prior to randomization:
- Absolute neutrophil count (ANC) $\geq 1.5 \times 10^9/L$. Granulocyte colony-stimulating factor (G-CSF) cannot be administered within 2 weeks (14 days) prior to randomization.
 - Platelet count $\geq 100 \times 10^9/L$
 - Hemoglobin ≥ 9.0 g/dL. No transfusions are allowed within 2 weeks (14 days) prior to randomization.
 - The creatinine clearance is ≥ 45 mL/min (refer to [Attachment 5](#) for the Cockcroft-Gault formula)
 - Proteinuria ≤ 1000 mg in 24 hours (if routine urinalysis indicates $\geq 2+$ proteinuria)
 - Total bilirubin below upper limit of normal (ULN) (except for patients with Gilbert's Syndrome, who must have a total bilirubin < 3 mg/dL)
 - Alanine aminotransferase/aspartate aminotransferase (AST/ALT) $\leq 3.0 \times$ ULN; if the liver has tumor involvement, AST and ALT $\leq 5.0 \times$ ULN are acceptable.
 - The patient has an adequate coagulation function as defined by International Normalized Ratio (INR) or prothrombin time (PT) $\leq 1.5 \times$ ULN, and partial thromboplastin time (PTT or aPTT) $\leq 1.5 \times$ ULN if not receiving anticoagulation therapy. For patients receiving anticoagulants, exceptions to these coagulation parameters are allowed if they are within the intended or expected range for their therapeutic use. Patients must have no history of active bleeding (defined as within 14 days of first dose of study drug) or pathological condition that carries a

high risk of bleeding (for example, tumor involving major vessels or known esophageal varices).

- [11] The patient has left ventricular ejection fraction (LVEF) $\geq 50\%$ assessed within 28 days prior to randomization.
- [12] Females of child-bearing potential must have a negative serum pregnancy test within 7 days prior to randomization.

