5.1. Sample Size

The primary objective of this trial is to compare doxorubicin plus olaratumab versus doxorubicin plus placebo with respect to OS in 2 populations:

- (1) Patients with advanced or metastatic STS not amenable to treatment with surgery or radiotherapy with curative intent
- (2) Patients with advanced or metastatic LMS not amenable to treatment with surgery or radiotherapy with curative intent

Population (1) will be analyzed for efficacy among all randomized study patients (the intent-to-treat [ITT] population). Population (2) will be analyzed as the subset of randomized patients with LMS. Therefore, this document will consider Population (1) as synonymous with the ITT study population, and refer to Population (2) as the “LMS population”. The study will be considered a positive study if either the ITT or LMS populations (or both) show a statistically significant improvement in OS with the regimen of doxorubicin plus olaratumab.

The study will enroll 460 patients in 1:1 randomization (230 patients in the investigational arm and 230 patients in the control arm). Enrollment will be conducted so that approximately 200 patients with LMS and 260 patients with other (non-LMS) histology will be randomized. The final analysis will occur only when both a minimum of 131 OS events have been observed in randomized patients with LMS and a minimum of 322 OS events have been observed in randomized patients overall.

See Section 5.11.1 for a detailed description of the statistical testing plan according to the graphical approach of Maurer and Bretz (2013).

The overall type I error rate for the study is controlled at 0.025 (1-sided). The associated sample sizes for the hypotheses that form the primary objective are based on the initial allocation of alpha (OS ITT $\alpha = 0.02$ and LMS $\alpha = 0.005$, 1-sided). One interim efficacy analysis will be performed at 194 ITT OS events.

If the ITT OS hazard ratio (HR) is assumed to be 0.723, and assuming 322 ITT OS events, a log-rank comparison of OS between study arms in the ITT population will have 80% power at the nominal alpha of 0.02. Assuming 30% censoring, a total sample size of 460 randomized patients is required.

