5.11.3. Secondary Efficacy Analyses

5.11.3.1. Supportive Analyses of Primary Efficacy Endpoint

The following supportive analyses of OS will be performed:

- HR for treatment effect will be estimated using an unstratified Cox PH model.
- As a sensitivity analysis, the primary OS analysis will be repeated using stratification based on the eCRF values.
- HR for treatment effect will be estimated using a multivariate Cox PH model, stratified by the randomization factors, with covariates selected among the additional factors listed in Section 5.3 using a stepwise selection method. Factors will be analyzed as continuous variables, except for those factors specifically identified with categories in Section 5.3. The stepwise selection will use an entry p-value <0.05 and exit p-value ≥ 0.10 . The “assigned treatment arm” variable will not be used within the stepwise procedure but rather added to the final model. The OS HR for treatment effect and corresponding 95% CI will be estimated from the final model. Any covariate listed in Section 5.3 may be removed from this planned analysis if the number of patients representing 1 level of that variable is insufficient or data collected on that variable are insufficiently complete.

- As a sensitivity analysis, the primary OS analysis will be repeated for the Per-Protocol population.
- To evaluate whether new anticancer treatment affects OS, a sensitivity analysis will be conducted censoring OS at a start date of new anticancer therapy.
- To evaluate whether the number of cycles of doxorubicin affects overall survival, a comparative OS sensitivity analysis will be conducted that excludes patients completing less than 4 cycles of doxorubicin (then repeated excluding those completing less than 5 cycles, then 6 cycles).
- Efficacy analyses (OS, PFS, and ORR) will be analyzed for a subset of patients who have received at least one dose of either olaratumab or placebo monotherapy after discontinuation of study treatment with doxorubicin. Baseline characteristics and drug exposure will be summarized as supportive analyses for this subgroup of patients receiving monotherapy.

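### SAP 5.11.4 sets albumin and platelet subgroup cuts that, as printed, put every patient on one side, so these two OS and PFS contrasts would be uninformative

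*SAP*

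**What the plan says.** SAP 5.11.4 states that "OS and PFS HR for treatment effect (with 95% CIs) will be estimated using an unstratified Cox PH model" in each of 23 listed subgroup factors. Most of the laboratory and continuous factors are split at the median, which needs no unit. Albumin, platelets and leukocytes instead have fixed numerical cuts:

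- Albumin: "albumin level (above and below 35 g/dL".
- Platelets: "platelets (above and below 350", followed by μ liters as the unit.
- Leukocytes: "leukocytes (above and below 10,000", followed by the same unit.

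The same section adds a rule for sparse levels: "If a level of a factor consists of fewer than 5% of randomized patients, analysis within that level will be omitted".

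No other place gives a cut or a unit for the albumin or platelet subgroups. SAP 5.3 lists both as covariates without units, and Protocol Attachment 2 names the tests without units or ranges. On the scale of the platelet count, Protocol 7.1, criterion 10, requires "Platelet count $\geq 100 \times 10^9/L" at entry, and Protocol 9.4.1.1 writes the same number as 100,000/μL.

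**The concern.** For a factor with a fixed cut, the number and its unit are the whole specification. If no patient can fall on one side, the planned comparison of treatment effect between levels does not exist, and the forest plot shows one row that looks like a subgroup result but is the overall result. SAP 5.11.4 gives the purpose of these analyses as checking internal consistency and looking for heterogeneity of effect. For albumin and platelets that purpose would not be met. If the cuts are instead reinterpreted after treatment codes are open, they can no longer be called prespecified.

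**Working it through.** **Inputs**

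- Albumin cut: 35 g/dL (SAP 5.11.4).
- Platelet cut: 350, unit μ liters (SAP 5.11.4). As printed this is a volume; the nearest literal reading is 350 per μL.
- Leukocyte cut: 10,000, same unit (SAP 5.11.4).
- Platelet floor at entry: 100 x 10^9/L (Protocol 7.1).
- Planned size: "The study will enroll 460 patients in 1:1 randomization" (SAP 5.1).
- Serum albumin range: 1 to 7 g/dL. This is an assumption, made deliberately wide; the documents give none.

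**Step 1. Reproduce the protocol's own platelet equivalence.** One litre is 10^6 μL, so 100 x 10^9/L ÷ 10^6 = 100,000/μL. This matches the figure in Protocol 9.4.1.1.

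**Step 2. Platelets against the cut.** 100,000 ÷ 350 = 285.7. The lowest eligible count is about 286 times the cut, so every eligible patient is above it. Put the other way, 350/μL is 0.35 x 10^9/L.

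**Step 3. Albumin against the cut.** 35 g/dL x 10 = 350 g/L. The top of the assumed range is 7 g/dL, and 35 ÷ 7 = 5, so every patient is below the cut. The same holds for any assumed upper limit below 35 g/dL.

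**Step 4. Leukocytes.** 10,000/μL x 10^6 ÷ 10^9 = 10 x 10^9/L. With the missing *per* supplied, this cut works. Only the notation is wrong.

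**Step 5. Apply the 5% rule.** 0.05 x 460 = 23 patients. The empty level of each factor has 0, which is below 23, so analysis within it is omitted.

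**Step 6. What remains.** The other level contains every patient with a baseline value. An unstratified Cox model fitted there is the overall unstratified model, which SAP 5.11.3.1 already plans for OS and 5.11.3.2 carries over to PFS. Apart from patients with a missing value, the two hazard ratios are the same number.

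**Step 7. Check that plausible corrections work.** Albumin 35 g/L ÷ 10 = 3.5 g/dL, inside the assumed range. Platelets 350 x 10^9/L ÷ 10^6 = 350,000/μL, above the floor and 1,000 times the literal cut. Both levels of each factor can then be populated. The size of each split cannot be computed, because the documents give no distributions.

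**The case against.** The strongest reply is that these are obvious slips that any programmer would correct. SAP 5.11.4 allows further subgroup analyses as appropriate and SAP 5.2 allows further exploratory analyses, so a sensible split needs no change of method. That limits the damage, but an analysis added later is not the prespecified one.

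The platelet string may also be damaged. The leukocyte line has the same odd unit, the documents were read from PDF, and the protocol writes platelet counts as multiples of 10^3/μL, so a multiplier or a slash could have been lost. This stands as a caveat for platelets. It does not explain 35 g/dL, which is legible and complete.

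A third reply is that the multivariate OS model in SAP 5.11.3.1 covers both factors: "Factors will be analyzed as continuous variables, except for those factors specifically identified with categories in Section 5.3". The cuts indeed do not touch that model. But it adjusts for albumin and platelets as covariates, with treatment added at the end, and specifies no treatment-by-factor interaction. It does not replace the subgroup contrast.

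Finally, eligibility rests on local laboratory values (Protocol 10.4.1), and an inadvertently enrolled patient may stay in the study (Protocol 7.3.1). Strictly, then, the platelet statement covers eligible patients rather than all patients. A gap of 286-fold makes the difference one of wording.

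**Conclusion.** Wrong as written, with minor impact. Followed literally, the albumin and platelet cuts each leave one level empty, and the level that remains repeats the overall unstratified OS or PFS hazard ratio. Two of 23 planned subgroup factors are affected. The platelet result follows from the documents if the unit is read as per μL and the printed text is intact. The albumin result rests on the assumed serum range, but any credible range gives it.

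A reader might infer more than the documents support:

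- That both analyses vanish. The 5% rule removes only the empty level; the other is still reported, without information about heterogeneity.
- That g/dL is an invalid unit. It is a valid one; the fault is the number 35 attached to it, a tenfold error if g/L was meant.
- That the leukocyte cut fails too. It does not once read as 10,000/μL.
- That the trial's conclusions are at risk. SAP 5.6 controls type I error only for OS, PFS and ORR through the testing graph. These subgroups carry no alpha, and neither the primary nor the key secondary analyses use the cuts.

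**What to change.** Before the sponsor is unblinded to aggregate data, have the sponsor confirm the intended cut-points and correct SAP 5.11.4. Examples that would work are albumin above and below 35 g/L (3.5 g/dL) and platelets above and below 350 x 10^9/L (350 x 10^3/μL). For leukocytes, write 10,000/μL; the value itself need not change. If the source file of the SAP already shows the platelet multiplier, only the albumin line needs a change of substance.

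The cost is three short edits. No new data, no change of method and no change to sample size or alpha are needed.

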5.11.5. Analyses by Baseline Lung Lesions

Section 5.11.4 identified the presence or absence of lung lesions at baseline as one factor to be considered for efficacy subgroup analyses. Retrospective data analyses of the phase 2 study I5B-MC-JGDG (conducted after initiating enrollment of the phase 3 study I5B-MC-JGDJ, but prior to unblinding of aggregate phase 3 efficacy data) showed strong evidence of a statistical interaction for overall survival, between study treatment arm and the presence or absence of baseline lung lesions. A much stronger OS treatment effect was observed in patients with

baseline lung lesions than in patients without baseline lung lesions. These results suggest the hypothesis that olaratumab, when used as part of a treatment for patients with advanced or metastatic disease, may be generally more effective in patients with lung lesions than in patients without lung lesions; and therefore in this section we pre-specify analyses for the phase 3 JGDJ study to look for confirmation of this statistical interaction.

Statistical interaction should initially be evaluated by constructing a Cox model with main effects for (i) the assigned study treatment arm and (ii) radiologic evidence of baseline lung lesions, plus an interactive term for (iii) treatment arm by baseline lung lesions. Other terms for prognostic factors may be included as additional cofactors in the model as deemed appropriate depending on the strength of prognostic effect. Statistical interaction will be judged primarily based on the statistical significance of the interaction term in the model.

If the interaction is statistically significant, then separate Cox models should be constructed for patients with baseline lung lesions and for those without (and repeated for other time to event efficacy variables including PFS, nMFS, and time to new metastases). Also in the event of a statistically significant interaction, further exploratory analyses should be conducted to evaluate whether the interactive effect is consistent across histologic subtypes and across other key subgroups (e.g. men versus women, ECOG performance status 0 versus 1, etc.). These further exploratory analyses will be important for evaluating the clinical relevance of any observed statistical interaction.

Additional exploratory analyses will be conducted considering tissue and biomarker data with respect to lung lesions. For example, available tissue from lung lesion biopsies may be analyzed for PDGFR alpha expression. Depending on available data, these results may be analyzed for association with efficacy outcomes.

5.12. Post-Study Drug Discontinuation Therapy

The numbers and percentages of patients reporting post-study therapies will be provided overall, by type of therapy (surgery, radiotherapy, or systemic therapy), and by regimen for all systemic anticancer regimens used. Patients will also be analyzed by post-study systemic anticancer regimens with respect to whether the treatment was the first post-study regimen, second post-study regimen, etc.

5.13. Patient-Reported Outcome Analyses

For each instrument, percentage compliance will be calculated as the number of completed assessments divided by the number of expected assessments (that is, patients still on study). Percentage compliance will be summarized by treatment group and overall. Similarly, the reasons for non-compliance will also be summarized descriptively.

Time-to-event variables will be analyzed using stratified log-rank tests (analogous to the primary analysis) for comparisons between study arms, stratified Cox models (for between-arm statistics including the treatment HR), and Kaplan-Meier method (for within-arm statistics).

Data will also be summarized descriptively for all of the variables identified Section 5.2.1.3, including shift tables.

QLQ-C30

Percentages of patients categorized as “improved” will be summarized and compared between study arms. Maximum improvement and worsening scores will be analyzed as continuous variables and compared between study arms using analysis of covariance (with both parametric and non-parametric p-values reported).

For the Physical functioning (PF2) as well as Emotional functioning (EF) scales, the change from baseline will be further analyzed by using mixed-effect repeated measures models based on restricted maximum likelihood estimation. Fixed effects in the model will include study treatment arm, baseline score, cycle number, and interaction term for study treatment arm and cycle number. The variance-covariance matrix that results in the minimum Akaike Information Criterion (Akaike 1973) from among unstructured, variance components, auto-regressive, and compound symmetric will be incorporated in the model. To implement the variance structure, patients will be included in the model as a random effect. The magnitude of the main effects and interactions will be evaluated and discussed. Based on the model-based means (LSMeans) from the repeated measures model, treatment group contrasts will be tested for each cycle number separately. Treatment group contrasts also will be tested for the treatment group marginal means.

Floor and ceiling effects will be summarized for each of the 15 scales. The presence of a significant ceiling effect suggests that not much improvement is possible for that scale. Likewise the presence of a floor effect suggests that worsening is less likely.

Modified Brief Pain Inventory – short form (mBPI-sf)

Percentages of patients categorized as “improved” will be summarized and compared between study arms. Similarly, percentage of patients achieving a clinical pain response will be summarized and compared between study arms. The cumulative distribution of the percentage of pain responders by treatment arm as a function of time is to be presented graphically. Maximum improvement and worsening scores will be analyzed as continuous variables and compared between study arms using analysis of covariance (with both parametric and non-parametric p-values reported).

Individual pain items on the mBPI-sf (that is, worst, least, average, and current pain) will be described using descriptive statistics by treatment arm and cycle. A mixed effects repeated measures model will be applied to compare between treatment arms, which may be adjusted for other covariates. Similar analyses will also be conducted for the mean of 7 pain interference with function items.

EQ-5D-5L

The EQ-5D-5L responses for each item will be summarized by frequency and corresponding percentages by treatment arm and cycle. Descriptive statistics (mean, standard deviation, median, minimum and maximum) for the index and VAS will be calculated and presented by treatment arm and cycle. Additionally, the change from baseline will also be presented. The index score

between treatment arms will be compared using mixed models. The model will include baseline score as a covariate and an unstructured covariance matrix will be utilized. A similar analysis will be performed on the VAS scores.

Of interest is a significant time-by-group interaction for each of the items, addressing whether treatment group profiles are different over time (from randomization through the last assessment following discontinuation).

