5.2.1.3. Patient-Reported Outcome Analysis Variables

Three scales will be used to assess patient reported Quality of Life (QoL) outcomes: EORTC-QLQ-C30, Modified Brief Pain Inventory – short form (mBPI-sf), and EQ-5D-5L.

EORTC-QLQ-C30

The European Organisation for Research and Treatment of Cancer Quality of Life Questionnaire Core 30 version 3.0 (EORTC-QLQ-C30), a self-administered, cancer-specific questionnaire consisting of 30 questions with multidimensional scales.

Assessments will be scored according to the EORTC QLQ-C30 Scoring Manual (Fayers et al., 2001). The 30 items (Q1-Q30) of the QLQ-C30 are scored to obtain 15 scales (1 global health status/QoL scale, 5 functional scales, and 9 symptom scales/items). A linear transformation is used to obtain scales ranging from 0 to 100 where:

- A high score for a functional scale represents a high / healthy level of functioning.

- A high score for the global health status / QoL represents a high QoL.
- A high score for a symptom scale / item represents a high level of symptomatology / problems.

EORTC QLQ-C30 (Version 3) Summary of Fifteen Scales and Scoring

Scale	Raw Score: Mean of items	Score
Global health status/QoL (QL2)	Q29, Q30	$\{1-(\text{Raw Score}-1)/6\} \times 100$
Functional scales		
Physical functioning (PF2)	Q1-Q5	
Role functioning (revised) (RF2)	Q6, Q7	
Emotional functioning (EF)	Q21 - Q24	$\{1-(\text{Raw Score}-1)/3\} \times 100$
Cognitive functioning (CF)	Q20, Q25	
Social functioning (SF)	Q26, Q27	
Symptom Scales		
Fatigue (FA)	Q10, Q12, Q18	
Nausea and vomiting (NV)	Q14, Q15	
Pain (PA)	Q9, Q19	
Dyspnoea (DY)	Q8	$\{(\text{Raw Score}-1)/3\} \times 100$
Insomnia (SL)	Q11	
Appetite loss (AP)	Q13	
Constipation (CO)	Q16	
Diarrhea (DI)	Q17	
Financial difficulties (FI)	Q28	

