Worsening will be defined as an increase of at least 10 points for the symptom scales or a decrease of at least 10 points for the functional scales and the global health status/QoL scale. Time to worsening will be calculated as the time from the first study drug dose (baseline date) to the first observation of worsening. If worsening is observed after a missing value, it may be assumed that the worsening occurred at the time of the missing value. Otherwise, the patient may be considered lost to follow-up and censored at the date of last assessment. Patients with no post-baseline assessment will be censored at the baseline date. Patients who have the worst possible score at baseline or a missing baseline assessment (i.e. no assessment prior to or on the day of the first study drug dose) will not be included in this analysis. In addition, the following variables will be derived for each scale score:

- For each patient, change from baseline will be calculated for every postbaseline assessment by subtracting the baseline assessment result from the current assessment result.
- Maximum improvement and maximum worsening scores (over baseline) will be determined from the set of all postbaseline change scores.

- Maximum improvement and maximum worsening scores (over an assessment at start of monotherapy) will be determined from a set of change scores from 2nd monotherapy cycle onwards.
- A patient first improving over baseline by 10 points or more without prior worsening of 10 points or more will be categorized as having “improved” for that particular scale score during the study. A change of ≥ 10 points on the 100-point scales is considered clinically meaningful (Osoba et al. 1998)

Modified Brief Pain Inventory – short form (mBPI-sf)

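### The between-arm test of maximum PRO improvement and worsening (SAP 5.13) favours finding a difference whenever one arm completes more questionnaires

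*SAP*

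**What the plan says.** SAP 5.2.1.3 defines the variables identically for the QLQ-C30 scales and the mBPI-sf worst-pain score: "Maximum improvement and maximum worsening scores (over baseline) will be determined from the set of all postbaseline change scores". A second pair of maxima, measured from the start of monotherapy, "will be determined from a set of change scores from 2nd monotherapy cycle onwards". SAP 5.13 then says, once for each instrument: "Maximum improvement and worsening scores will be analyzed as continuous variables and compared between study arms using analysis of covariance", with parametric and non-parametric p-values. The QLQ-C30 version covers many outcomes: "The 30 items (Q1-Q30) of the QLQ-C30 are scored to obtain 15 scales", six of which are single items.

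Protocol 10.2 collects the forms on Day 1 of every cycle and at the 30-day visit. After that they are 6-weekly until PD, then 3-monthly, 6-monthly and annual. The footnote to SAP Table JGDJ.5.5 assumes PFS medians of 4.5 months (control) and 7.15 months (experimental). SAP 5.3 lists strata and possible covariates; neither the number of assessments nor time on study is among them.

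Other planned comparisons do not use the maxima:

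- Time to worsening: "Time-to-event variables will be analyzed using stratified log-rank tests (analogous to the primary analysis) for comparisons between study arms".
- mBPI-sf items and interference: "A mixed effects repeated measures model will be applied to compare between treatment arms, which may be adjusted for other covariates".
- QLQ-C30 physical and emotional functioning: a repeated-measures model by cycle, in which the covariance structure with the smallest AIC "from among unstructured, variance components, auto-regressive, and compound symmetric will be incorporated in the model".

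**The concern.** A maximum over 15 noisy scores tends to exceed a maximum over 10, even if the scores have the same distribution at every visit. If olaratumab delays progression as the design assumes, its patients complete more forms. Both their maximum improvement and their maximum worsening are then pushed outward by observation time alone.

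The test is a valid comparison of the most extreme score ever recorded. It does not test whether PRO scores differ at any visit, and the SAP does not say which question is meant. PROs are a stated secondary objective, so a small p-value for maximum improvement could be read as a quality-of-life or pain benefit when it reflects longer time on treatment.

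**Working it through.** **Stated figure.** The documents give no operating figure for this test beyond the two-sided 0.05 in SAP 5.2. The check therefore asks whether it holds 5% when the score distributions are the same in both arms at every visit.

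**Forms per patient.** Assume exponential PFS (hazard ratio 4.5/7.15 = 0.629), one form every 21 days (21/30.4375 = 0.690 months) and a 36-month cutoff (52 cycle visits). The probability of remaining PD-free over one cycle is q = 2^(−0.690/m). Expected forms with treatment to PD are q(1−q^52)/(1−q) + 1, the last term being the 30-day form.

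- Control, m = 4.5: 8.92 × (1 − 0.004) + 1 = 9.9.
- Olaratumab, m = 7.15: 14.46 × (1 − 0.031) + 1 = 15.0.

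**Null simulation.** There were 2000 trials per setting, with Monte Carlo SE about 0.5 points at a 5% rate and 1 point at 30%. The PFS medians, form schedule and requirement for at least one postbaseline form come from the documents. The rest is assumed:

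- score SD 25;
- stable between-patient share of variance 0.2–0.8;
- serial correlation 0, 0.7 or 0.9 per cycle;
- non-PD stopping from none to a 3-month median;
- compliance 60–100%;
- long-term form return 0, 50 or 100%.

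Maximum improvement and maximum worsening were each tested by ANCOVA on arm and baseline. Ranges cover the inputs tried and are not bounds.

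| Continuous score, 200 per arm unless stated | Rejection at 5% |
|---|---|
| All treated to PD (9.9 vs 15.0 forms) | 39–59% |
| Non-PD stopping, median 12 or 9 months, 90% compliance | 18–33% |
| 6-month stopping, 80% compliance, no long-term forms (4.7 vs 5.9 forms) | 12–19% |
| Same, with long-term forms | 17–30% |
| Equal OS, all long-term forms returned | 14–28% |
| 3–4-month stopping, 60–80% compliance, no long-term forms | 7–11% |
| No stable patient component, treated to PD, 230 per arm | 71–73% |
| **Equal PFS medians** | **4.7–5.9%** |

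Rank-based p-values gave 12–56% outside the two corner settings (3–4-month stopping; no stable component). At 230 per arm, treated to PD with independent visit noise, the rate was 40–61% for within-patient correlations of 0.95 down to 0.3. At 100 per arm (the LMS size) it was 23–26%. The lowest rate found under this strict null was 6–7%, with 3-month stopping plus long-term forms. The equal-median row isolates the cause: the ANCOVA is sound, and unequal observation inflates it.

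**Other score types** (treated to PD / 9-month / 6-month stopping):

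- Bounded multi-item scores and 0–10 worst pain: 34–48% / 19–24% / 12–15%.
- Four-level single items, worsening: 29–38% / 14–19% / 10–13%.
- Four-level single items, improvement: 11–32% / 8–17% / 7–11%.

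**Time trends.** If scores fall 0.5 SD from 6 weeks before PD (not a strict null), the effect moves to improvement. With 9-month stopping, worsening rejects 7% and improvement 44–50%; treated to PD, 20–21% and 61–69%. A common decline of 0.05 SD per visit in both arms, treated to PD, gives 89–93% for worsening and 17–18% for improvement.

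**Smaller PFS difference.** Medians of 4.5 and 5.5 months give 12–14% treated to PD and 7–9% with 9-month stopping.

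**Monotherapy maxima.** Suppose monotherapy starts at Cycle 9 Day 1 (day 168 = 5.52 months). PD alone leaves 2^(−5.52/4.5) = 43% against 2^(−5.52/7.15) = 59%, or 98 and 135 of 230. The first usable score is one cycle later (day 189 = 6.21 months): 38% against 55%. The same test rejects 20–32% treated to PD and 6–15% with stopping.

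**Alternatives under the same null.**

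- Repeated-measures model with the SAP's four covariance candidates and AIC choice: 4.9–6.2%. Forcing AR(1) gave 7.7–9.0%.
- Log-rank on time to a 10-point worsening (unstratified): 4.5–8.0%.
- Maximum over Cycles 2–4 in patients with all three forms: 3.4–6.6%, or 4.9–7.4% with the fall before PD.
- Truncating both arms at eight cycles: still about 14%, because fewer control patients reach those cycles.

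**The case against.** The strongest reply is that this is a choice of estimand. The SAP never states a by-visit null for the maxima, and by-visit contrasts are tested elsewhere in 5.13. With equal PFS the test holds its level. That is correct, but the SAP does not say that the most extreme recorded score is the target, and the label invites the other reading.

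Unequal follow-up will also be visible. SAP 5.13 says "Percentage compliance will be summarized by treatment group and overall", which alone would not reveal it, but Protocol 12.2.10 adds compliance and data summaries by arm and time point, and SAP 5.14.1 reports infusions and duration of therapy. This stands: form counts could largely be derived from planned output. It does not change the p-values.

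The largest rates need every patient treated to PD and scores unrelated to progression. With the fall before PD, 6-month stopping and 80% compliance, maximum worsening rejected only 4.7% (600 trials), although maximum improvement stayed at 37%. This stands as a limit on the worsening half of the claim.

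The alternatives are not perfect either: up to 8.0% for time to worsening and 7.4% for the early window. Their log-rank check was unstratified and did not use the mBPI-sf analgesic rule. They are still far nearer 5% than the maxima in most settings. The between-arm comparisons of percentages improved and of pain response also have no common window; they were not tested here.

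**Conclusion.** The concern holds. Under the SAP's own PFS medians and a strict by-visit null, every setting tried exceeded 5%: from 6–7% at the lowest, through roughly 12–33% with moderate stopping and missing forms, to 39–59% if all are treated to PD. The size is not determined by the documents, which give no PRO variance, correlation, compliance or non-PD stopping rate. Inflation requires a PFS difference and visit-to-visit variation within patients. A decline in scores near PD shifts the effect mainly to maximum improvement.

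The consequence is moderate. SAP 5.6 leaves these tests outside the controlled family, and OS, PFS and ORR are unaffected. The spurious differences, about 1–5 points on the QLQ-C30 and 0.1–0.3 on worst pain, are below the SAP's 10-point and 2-point thresholds. The change is worth making because PROs are a secondary objective and it is cheap.

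**What to change.** In SAP 5.13, for both instruments, report maximum improvement and maximum worsening descriptively by arm, beside the distribution of completed assessments per patient, with no between-arm p-value. Treat the monotherapy-baseline maxima the same way; an early window cannot apply to them.

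For between-arm inference, rely on the planned time-to-worsening analyses, the mBPI-sf mixed model, and the physical and emotional functioning model. Extend that last model to the other 13 QLQ-C30 scales, keeping its AIC choice of covariance.

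If a test of the extreme is still wanted, restrict it to a short common window, such as Cycles 2–4 in patients with all three forms, and state the cost. By Cycle 4 Day 1 (day 63 = 2.07 months), PD alone excludes 1 − 2^(−2.07/4.5) = 27% of control and 1 − 2^(−2.07/7.15) = 18% of olaratumab patients. With 9-month stopping and 90% compliance this becomes 55% and 49%; with 6-month stopping and 80% compliance, 71% and 67%. This is the weaker option.

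The main change costs SAP wording and re-use of an existing model. What is lost is a simple summary p-value.
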